9.4.2 Primary endpoints

The primary endpoints are defined in Section 3.

All AEs will be coded using the most recent version of Medical Dictionary for Regulatory Activities (MedDRA[®]) coding system to get a system organ class (SOC) and preferred term (PT) for each AE.

Reactogenicity

Solicited local and systemic reactions (from the subject diary) will be summarized using the Safety Set. In general, solicited reactions will be analyzed for each immunization, i.e.:

• Up to 7 d after each IMP injection

For each injection, the number and percentage of subjects reporting at least one local reaction or systemic reaction (i.e., solicited data collected using subject diaries) will be summarized for each of the following types using the Safety Set:

BioNTech SE	Clinical Trial Protocol
Confidential	BNT162-14

- Any local reactions or systemic reactions
- Grade ≥3 local reactions or systemic reactions

Moreover, the number and percentage of subjects reporting at least one local reaction will be summarized by worst grade using the Safety Set.

Unsolicited TEAEs

For Group A and Group B immunology subset, the number and percentage of subjects reporting at least one TEAE (defined in Section 10.3.1) will be summarized by PT nested within SOC for each of the following AE types using the Safety Set:

- Any AE
- Related AE
- Grade of AE
- Related Grade ≥3 AE
- Any solicited AE that continues past 7 d post-trial injection or is an SAE, or AE that fits the definition of a solicited AE but starts after Day 8
- Any SAE
- Related SAE
- AESI

Moreover, the number and percentage of subjects with any AE will be summarized by worst grade by PT nested within SOC.

For Group B, AESIs and SAEs will be analyzed.

Additional AE analyses may be described in the SAP.

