The following TEAE types will be analyzed for Group A and the immunology subset of Group B:

- Any TEAE
- Related TEAE, i.e., suspected unexpected serious adverse reactions (SUSARs) which will be described in safety reports
- Any Grade ≥3 TEAE
- Any related Grade ≥3 TEAE
- Any treatment emergent serious adverse event (TESAE)
- Related TESAE
- TEAESI

- TEAEs linked to confirmed COVID-19 cases (TEAEs with preferred term = 'COVID-19')
- Deaths

The following AE types will be analyzed for all groups if applicable:

- Any AE
- Related AE
- Any Grade ≥3 AE
- Any related Grade ≥3 AE
- Any serious adverse event (SAE)
- Related SAE
- AESI
- Related AESI
- Any AEs linked to confirmed COVID-19 cases (AEs with preferred term = 'COVID-19')
- Deaths

Overall summary of TEAEs

For Group A and the immunology subset of Group B, the number and percentage of subjects reporting at least one TEAE and the number of TEAEs will be summarized for all TEAE types defined above overall.

For Group B, the number and percentage of subjects reporting at least one

- SAE
- AESIs

will be summarized.

For Group A and the immunology subset of Group B, the number and percentage of subjects reporting at least one TEAE and the number of TEAEs will be summarized by PT nested within SOC for each of the following AE types: Any TEAE, Related TEAE, Any TESAE, Related TESAE, TEAEs leading to treatment discontinuation, solicited TEAEs and fatal TEAE.

For Group B, the number and percentage of subjects reporting at least one TESAE will be summarized by PT nested within SOC.

If a SOC and PT is reported more than once for a subject, the subject will only be counted once for this SOC and PT at the worst grade level. All TEAE summary tables will be sorted alphabetically by SOC and PT within SOC.

TEAE by grade

For Group A and the immunology subset of Group B, the number and percentage of subjects with TEAEs and TESAEs will be summarized by worst grade by PT nested within SOC by time interval.

For Group B, the number and percentage of subjects with TESAEs will be summarized by worst grade by PT nested within SOC.

The worst grade will be counted if a TEAE is reported more than once by the same subject for this SOC and PT.

AEs

The number and percentage of subjects reporting at least one AE and the number of AEs will be summarized for the above defined AE types for all groups.

SAEs

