The number and percentage of subjects reporting at least one SAE and the number of SAEs will be summarized by PT nested within SOC for each of the following AE types: Any SAE, Related SAE, fatal SAE and related fatal SAE.

Non-SAEs

The number and percentage of subjects reporting at least one non-SAE and the number of non-SAEs with >5% within any arm or reporting group will be summarized by PT nested within SOC.

AE listings

All TEAEs of subjects that withdrew due to AE, SAEs, and AESIs will be listed. The duration of an AE will be calculated in hours. If for an AE the time is missing then the duration will be calculated in days.

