7.1. Appendix 1: Changes to protocol-planned analyses

Instead of AEs by grade, the overall AE table will include AEs with Grade \geq 3.

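### SAP 6.4.3 omits two of the eight by-preferred-term AE tables planned in protocol 9.4.2 (related Grade ≥3 AEs and AESIs), and Appendix 7.1 declares neither change

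*SAP*

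**What the plan says.** Protocol 9.4.2 (Primary endpoints, Unsolicited TEAEs) says that in Group A and the Group B immunology subset the number and percentage of subjects with at least one TEAE "will be summarized by PT nested within SOC for each of the following AE types using the Safety Set". Eight types follow. The fourth is "Related Grade ≥3 AE" and the last is AESI.

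SAP 6.4.3 keeps "Any related Grade ≥3 TEAE" among its TEAE types, and also keeps treatment-emergent AESIs. For Group A and the immunology subset, numbers of subjects and of events "will be summarized for all TEAE types defined above overall". The tables by PT within SOC are limited to a separate list of seven types: "Any TEAE, Related TEAE, Any TESAE, Related TESAE, TEAEs leading to treatment discontinuation, solicited TEAEs and fatal TEAE". Neither related Grade ≥3 events nor AESIs are in it. A further table covers severity: "subjects with TEAEs and TESAEs will be summarized by worst grade by PT nested within SOC by time interval".

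On AE listings, SAP 6.4.3 says: "All TEAEs of subjects that withdrew due to AE, SAEs, and AESIs will be listed".

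Section 1 of the SAP states that changes from the protocol are recorded in Appendix 1 (Section 7.1). That appendix has one entry: "Instead of AEs by grade, the overall AE table will include AEs with Grade" 3 or above.

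**The concern.** The trial's primary objective is safety and tolerability, and neither document tests a hypothesis, so the descriptive safety tables are the primary result. A non-serious event that is Grade 3 or worse and judged related to the vaccine is one that a reader would want named, particularly in Group A, where BNT162b2s01 and Comirnaty are compared by randomization. The protocol planned a table that names such events, and the SAP does not produce it.

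The omission could also pass unnoticed. The SAP points readers to Appendix 7.1 for changes, and the one entry there concerns a different item. Protocol 9.4 requires the trial report to describe departures from the final SAP; a table that the SAP itself leaves out is not such a departure.

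**Working it through.** No figure in the plan is in dispute, so the check is a comparison of the two lists, followed by a test of whether the remaining outputs can replace what is missing.

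**1. Item-by-item comparison (Group A and immunology subset)**

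| Protocol 9.4.2 type, by PT within SOC | By PT in SAP 6.4.3? |
|---|---|
| Any AE | Yes (any TEAE) |
| Related AE | Yes (related TEAE) |
| Grade of AE | Yes (worst grade by PT) |
| Related Grade ≥3 AE | No, overall count only |
| Solicited AE that is prolonged, late or serious | Yes (solicited TEAEs) |
| Any SAE | Yes (TESAE; also SAE) |
| Related SAE | Yes (related TESAE; also related SAE) |
| AESI | No, overall count and listing |

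Covered: 6. Missing: 8 − 6 = 2.

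**2. Is either omission declared?** The single entry in Appendix 7.1 concerns the overall AE table and replaces its by-grade rows with Grade ≥3 rows. It corresponds to the protocol's grade item. It does not mention removing a by-PT table for related Grade ≥3 events or for AESIs.

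**3. Can the related Grade ≥3 table be rebuilt from the others?** Related TEAE by PT carries no grade, and worst grade by PT carries no relatedness. For one PT in one arm, let n be the subjects with the event, r those with a related event and g those whose worst grade is 3 or higher. With one event per subject in that PT, the number x with a related Grade ≥3 event satisfies

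max(0, r + g − n) ≤ x ≤ min(r, g).

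Illustration with assumed counts n = 6, r = 4, g = 2: the lower bound is max(0, 4 + 2 − 6) = 0 and the upper bound is min(4, 2) = 2, so x may be 0, 1 or 2. The count is exact in special cases such as r = n, r = 0 or g = 0. If a subject can have several events under one PT, the lower bound weakens, because the related event and the severe event need not be the same one. An overall related Grade ≥3 count of zero would also settle every PT at zero.

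These bounds take the related TEAE table to cover all related TEAEs. In its list of types, SAP 6.4.3 equates related TEAEs with SUSARs. Applied literally, that would restrict the table to serious unexpected reactions and make it a poorer substitute.

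**4. What other outputs show**

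- Overall counts: SAP 6.1.1 reports Group A by vaccine and by HIV status within vaccine, and the immunology subset by transplant status.
- Serious related events: by PT, in the related TESAE and related SAE tables.
- Solicited Grade ≥3 reactions within 7 days: by reaction term (SAP 6.4.1 and 6.4.2).
- SAEs and AESIs: named in the AE listing sentence.

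What remains uncovered is the identity, by PT and arm, of related Grade ≥3 TEAEs that are neither serious nor AESIs and occur in subjects who did not withdraw because of an AE.

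**5. Population.** The maximum number of subjects the two tables would cover is 90 (Group A) + 129 (immunology subset) = 219 (protocol 4.1, SAP 1.2).

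**The case against.** A reader might infer that severe vaccine-related events will be reported only as one pooled number, so that BNT162b2s01 and Comirnaty cannot be compared. The documents do not support that. The overall row gives subjects, percentages and event counts, and SAP 6.1.1 splits Group A by vaccine, so the frequency of this class can be compared between arms. Only the comparison by PT is missing.

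Nor is a primary endpoint lost. The endpoint is the proportion of subjects with at least one unsolicited TEAE, and the SAP analyzes it. The related Grade ≥3 table by PT is a supporting display. Severe reactogenicity, which is kept out of AE reporting unless serious, late or prolonged, is shown by term elsewhere.

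The strongest counter-argument is the general listing rule in SAP 6.1.1, under which important CRF data will be listed, with AE onset date given as an example of a sort key. Grade and causality are CRF items (protocol 10.3.1.7). If the rule is meant to reach every AE, each related Grade ≥3 event could be found by term and vaccine. This stands as a possibility. But the rule does not say that all AEs will be listed, and the sentence specific to AEs is narrower. A listing would also not be the summary that the protocol planned.

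Finally, declaring the removal in Appendix 7.1 would resolve the inconsistency. That is correct and is offered as an alternative below.

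**Conclusion.** The concern holds in a limited form. Two of the eight by-PT tables in protocol 9.4.2 are absent from SAP 6.4.3, and neither omission is declared. For AESIs the consequence is small, since they are counted overall and named for listing. For related Grade ≥3 events the gap is real but confined to non-serious, non-AESI TEAEs: their number in each arm will be known, but no committed output says which events they were. The figure of 219 is the maximum population covered by the tables, not a count of subjects affected; how many such events occur cannot be derived from the documents.

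This rests on two readings: that the seven-item by-PT list in the SAP is closed, and that the general listing rule does not by itself commit to all AEs. If the sponsor confirms a full AE listing with grade and relatedness, the loss of information largely disappears, and the undeclared departure from the protocol remains. It is worth correcting because the trial's safety result is purely descriptive and the correction is cheap.

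**What to change.** In SAP 6.4.3, add related Grade ≥3 TEAEs and treatment-emergent AESIs to the types summarized by PT within SOC for Group A and the immunology subset, using the reporting columns already set in SAP 6.1.1. Reword the AE listing sentence so that it covers all AEs, with TEAE flag, grade and relatedness shown.

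If the two tables were dropped on purpose, for example because few events are expected, say so and give the reason in Appendix 7.1, and keep the full listing so that the events can still be identified.

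In the same edit, remove or correct the wording that equates related TEAEs with SUSARs, so that the related TEAE table is not narrowed by accident.

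The cost is one or two further standard tables and a wider listing. The events are already coded, graded and assessed for causality, so no new data are needed.

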6.5. Secondary endpoint analyses

Secondary endpoints are neutralizing antibody titers and antibody titers (ELISA) to recombinant S1 and RBD protein derived from reference and SARS-CoV-2 variant B.1.351 (B.1.351 for Group A only) and SARS-CoV-2 functional cross-neutralization of variant B.1.351 to reference strain (for Group A only). All secondary analyses will be performed using the IMM and possibly additionally the IMMPP population, see Section 5.1.

Any COVID-19 vaccination that a subject received outside of this trial will be considered as concurrent event and all immunogenicity data assessed beyond this event will be excluded from the immunogenicity analyses.

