- k For subjects who receive non-trial SARS-CoV-2 vaccinations there will be no sampling in subsequent visits. Information about these vaccinations may be received outside of a planned visit and can be collected remotely, e.g., by phone. In such cases information on physical examination and vital signs can be skipped. However, AEs that occurred prior to administration of non-trial vaccine must be enquired and should be recorded as stated in footnote "i".
- Record any non-trial SARS-CoV-2 vaccinations that trial subjects receive during the trial in the CRF until the last trial visit.

Abbreviations: AE = adverse event; AESI = adverse event of special interest; CMI = cell mediated immunity; CRF = case report form; d = day; ELISA = enzyme-linked immunosorbent assay; EOT = end of trial; h = hour(s); IMP = investigational medicinal product; inj. = (IMP) injection; NAAT = nucleic acid amplification-based test; NATAB = neutralizing antibody titers and antibody binding; SAE = serious adverse event; SARS-CoV-2 = the virus leading to COVID-19; SoA = schedule of activities; WOCBP = women of childbearing potential.

		Page 12
BioNTech SE	Clinical Trial Protocol	Versio
Confidential	BNIT162 14	VEISIO
Connuential	DINT 102-14	Dete: 00 I

Page 12 of 91 Version: 4.0 Date: 20 JAN 2022

Table 2: Schedule of events for Immunology Subgroup of Group B (with two injections of Comirnaty) h

Activity	Visit 0	Visit 1	Visit 2	Visit 3	Visit 4	Visit 5	Visit 6 ^{I, m}	Visit 7 ^{I, m, o}	Early termination
Week(s)			1	3	4	7	12	26	
Day	-30 to -1	1	8+2	22±3	29+7	50±7	85±10	182±20	
	(Screening)	(Day of inj. 1; pre-dose except IMP injection)	(~7 d post inj. 1)	(~21 d post inj. 1; pre-dose except IMP injection)	(~7 d post inj. 2)	(~28 d post inj. 2)	(~63 d post inj. 2)	(~161 d post inj. 2 EOT Visit)	
Collect informed consent	Х						X m	X m	
Assess inclusion/exclusion criteria compliance	Х	X (review)							
Collect demographic and medical history	Х	X (update)							
Physical examination	Х	X a	X a	X a	X a			X a	X a
Vital signs, body weight ^b	Х	Хc		Хc					
Urine pregnancy test for WOCBP	Х	х		х				х	х
Blood draw for clinical laboratory (15 mL) ^d	Х								
Allocation to IMP		х							
IMP injection, then observe subjects for ~1 h		х		X ^h					
Subject hotline availability	Start	=>	=>	=>	=>	=>	=>	End	(End)
Oral swabs for NAAT-based SARS-CoV-2 for screening ^f	X e	X e							
Oral swab for NAAT-based SARS-CoV-2 testing for surveillance			х	x	х	Х	х	х	x

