4.2 Scientific rationale for the trial design

The scientific rationale for this open-label trial is the following:

- to describe changes in vaccine-induced durability and T cell, B cell and antibody breadth to SARS-CoV-2 antigens before and after booster vaccines;
 - to assess if booster vaccines improve immune responses against variant B.1.351;
 - to describe changes in vaccine-induced correlates of protection (if identified from other BNT162 vaccine studies);
- to assess safety of additional BNT162 booster vaccines;
- to describe sequences of SARS-CoV-2 infections to increase understanding of the current SARS-CoV-2 strains in circulation and document if potential signs of immune pressure from vaccines, genetics, etc. on the virus are observed; and
- to assess changes in immune responses in transplant subjects with 3rd and 4th vaccinations.

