7.2 Trial subject discontinuation or withdrawal from the trial

A trial subject may withdraw from the trial at any time at his/her own request or may be discontinued from the trial at any time at the discretion of the investigator for safety, behavioral, compliance, or administrative reasons. Withdrawals are expected to be uncommon.

Reasons for discontinuation from the trial include the following:

- Refused further trial procedures
- Lost to follow-up
- Death
- Trial terminated by sponsor
- SAEs thought related to the vaccine
- Trial subject request
- Investigator request
- Important protocol deviation per the investigator after consultation with the Medical Monitor
- A Group B transplant subject who receives a non-trial SARS-CoV-2 vaccination

If the trial subject withdraws consent for data processing, the sponsor may retain and continue to use any data collected before such a withdrawal of consent.

For trial subjects who withdraw consent, the investigator must clarify whether consent for research sample storage/processing (if given) is also withdrawn. If yes, then they must be informed that any research samples collected will be destroyed. The investigator must document research sample destruction in the Investigator's Site File (ISF) and inform the sponsor about the withdrawal of consent immediately.

If possible, permanently discontinued trial subjects will complete all assessments planned for the Early Termination Visit.

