6.1. General considerations

No formal statistical testing will be done.

Unless otherwise specified, analyses will be based on data pooled across all study sites within the BNT162-14 trial.

Data assessed after a vaccination with a non-trial SARS-CoV-2 vaccine will be excluded from all statistical analyses (tables and listings) accordingly.

Notes:

- Data assessed on the same day as the non-trial vaccination will remain in the analysis.
- If the date of non-trial vaccination is missing, but month and year information is available, data assessed after the last day of the respective month will be excluded from statistical analysis.

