6.1.1. Tables and listings

Tables

In general, data will be summarized as follows:

- Group A by vaccine [Comirnaty[®], BNT162b2s01], and total
- Group A subjects having received Comirnaty[®] by HIV infection status
- Group A subjects having received BNT162b2s01 by HIV infection status
- Group B by transplant status, and total
- Group B immunology subset by transplant status, and total

Descriptive summary tables and figures will be based on scheduled visits.

Continuous variables will be summarized using the following descriptive statistics: number of subjects with non-missing data (n), mean, standard deviation (SD), median, minimum (min) and maximum (max).

Descriptive statistics of titer and fold rise of titer will additionally include geometric mean and its two-sided 95% confidence interval (CI). The geometric mean titer (GMT) is calculated as the mean of the logarithm of the functional antibody titers, backtransformed into the original scale. Two-sided CIs will be obtained by calculating CIs using t-distribution for the mean of the logarithmically transformed assay results and transforming the limits back to the original scale.

Geometric mean fold rise (GMFR) is calculated as the mean of the difference of logarithmically transformed assay results (post vaccination time point – pre vaccination time point) and back-transformed into the original scale. Two-sided CIs will be obtained by calculating CIs using Student's t-distribution for the mean difference of the

logarithmically transformed assay results and transforming the limits back to the original scale.

Categorical variables will be summarized presenting absolute and relative frequencies (n and %) of subjects in each category (including the category 'missing' if applicable). Percentages will be calculated based on the number of subjects in the respective analysis set (N) as denominator if not stated differently. Percentages may be presented with exact 95% Clopper-Pearson CIs.

SDs and CIs will only be calculated if values from at least 3 subjects are available.

Listings

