6.1.3. Missing data

As a general rule, missing data will not be imputed (i.e., missing data will not be replaced but will be handled as "missing" in the statistical evaluation), with the following exceptions for summary analyses:

Clinical safety laboratory variables given as "<xx" will be evaluated as 0.5*xx in the summary tables. In the listings they will be displayed as "<xx" or similar.

Data values below lower limit of quantification (LLOQ) or detection (LLOD) will be imputed with 0.5*LLOQ or 0.5*LLOD, respectively, for the analysis of continuous data. Values above the upper limit of quantification (ULOQ) or detection (ULOD) will be imputed with 2*ULOQ or 2*ULOD, respectively, for the analysis of continuous data. In the listings they will be displayed as "<xx" or ">yy" as appropriate. In the tables they will be displayed as "<LLOQ"/("<LLOD" or ">ULOQ"/(">ULOD" in descriptive statistics (e.g., in mean, median, min, max) as appropriate. A footnote will be added to show the value of LLOQ or LLOD or ULOQ or ULOD.

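### Week 12 and Week 26 GMTs are available-case means over a changing set of subjects once people are vaccinated outside the trial; the SAP should name its target and add a supplementary repeated-measures model

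*SAP*

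**What the plan says.** SAP 6.5 treats a COVID-19 vaccination outside the trial as a concurrent event and says that "all immunogenicity data assessed beyond this event will be excluded from the immunogenicity analyses". SAP 6.1 has the same rule for every analysis: "Data assessed after a vaccination with a non-trial SARS-CoV-2 vaccine will be excluded from all statistical analyses (tables and listings) accordingly". The one exception is "Data assessed on the same day as the non-trial vaccination will remain in the analysis".

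Most of the later titers will never exist. Protocol 1.3 states in the schedule footnotes: "For subjects who receive non-trial SARS-CoV-2 vaccinations there will be no sampling in subsequent visits". The note sits on Visits 6 and 7 in Tables 1 and 2, on Visits 11 and 12 in Table 2a, and on Visit 7 only in Table 3. Some Week 12 samples may therefore be taken under Table 3 and then dropped by the SAP rule. For transplant subjects, Protocol 7.2 goes further and lists this as a reason for leaving the trial: "A Group B transplant subject who receives a non-trial SARS-CoV-2 vaccination".

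On missing values, SAP 6.1.3 says: "As a general rule, missing data will not be imputed". Its exceptions concern only values beyond assay or laboratory limits. On the estimator, SAP 6.1.1 says: "The geometric mean titer (GMT) is calculated as the mean of the logarithm of the functional antibody titers, backtransformed into the original scale". Intervals are t-based on the log scale, and n is the number of subjects with data. SAP 6.5.1 and 6.5.2 then draw GMT and GMFR as line plots over all visits.

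The only sensitivity analysis (SAP 6.6) is optional and drops infected subjects. Exploratory analyses, including the time-course objective, are left to another document (SAP 6.7).

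**The concern.** Durability is one of the trial's stated reasons. Protocol 4.2 opens with "to describe changes in vaccine-induced durability and T cell, B cell and antibody breadth", before and after boosting. Weeks 12 and 26 carry that information and are also the visits most exposed to loss through outside vaccination. Amendment 03 revised several protocol sections to deal with such vaccinations, so the sponsor expected them.

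A line joining the Week 4 and Week 26 GMTs invites the reader to see one cohort waning. If some subjects have left in between, the two points describe different people. If the leavers' earlier titers differed from the stayers', part of the drop or plateau reflects who remained. The t-based interval for Week 26 describes the stayers and does not allow for this.

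The earlier titers of those who left are in the database and count in the earlier GMTs, but the plan does not use them to inform the later ones. The SAP also does not say which quantity it wants: the enrolled cohort's titer had nobody been vaccinated elsewhere, or the titer of those not yet vaccinated elsewhere.

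**Working it through.** **What can be checked against the plan.** The documents give no titer SD, leaving rate, power or sample-size figure, so there is no stated figure to reproduce. The counts are consistent: Group A is 24 + 31 + 15 + 20 = 90, which is 60 and 30 under 2:1 allocation. The immunology subset is 36 + 30 + 15 + 48 = 129, of which 129 − 15 = 114 are not transplant subjects.

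**Assumptions (none is in the documents).** Log10 titer SD is 0.4 at each visit. The correlation between an early post-dose titer and Week 26 is ρ = 0.7. Leaving follows a logistic model in the early titer only. 30% or 40% leave, and the odds of leaving are 1.5 or 2 times higher per SD lower early titer. The comparison value is the full cohort's Week 26 GMT had nobody been vaccinated elsewhere.

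**GMT.** Let δ be the mean early titer among stayers, in SD units above the full-cohort mean, obtained by simulation. Then

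ratio of available-case to full-cohort GMT = 10^(SD × ρ × δ).

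| Odds ratio, share leaving | δ | 10^(0.4 × 0.7 × δ) | 95% CI coverage, n = 60 | 95% CI coverage, n = 114 |
|---|---|---|---|---|
| 1.5, 30% | 0.118 | 1.08 | 92% | 89% |
| 2, 30% | 0.191 | 1.13 | 87% | 78% |
| 2, 40% | 0.251 | 1.18 | 82% | 70% |

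Coverage comes from simulation with 6,000 replicates per case, with n counted before leaving. In the same simulations an estimator that also uses the early titer gave ratios of 0.998 to 1.002.

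**Wider grid.** With SD 0.4 or 0.6, correlation 0.6 or 0.8, 10% to 50% leaving and odds ratio 2 or 3, the available-case ratio ran from 1.04 to 1.63. With odds ratio 1 it was 0.997 to 1.003, so there is no bias when leaving is unrelated to titer. The estimator using the early titer stayed between 0.997 and 1.004 throughout. If subjects with higher titers leave, δ changes sign and the GMT is too low.

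**GMFR from baseline.** The same subjects stand in numerator and denominator, so much of the shift cancels. With r the correlation of baseline with the early titer (also assumed) and equal SDs,

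ratio for GMFR = 10^(SD × (ρ − r) × δ).

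- r = 0.7: the exponent is zero, so the ratio is 1.00.
- r = 0.5: 10^(0.08 × 0.118) = 1.02, 10^(0.08 × 0.191) = 1.04 and 10^(0.08 × 0.251) = 1.05.

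For r between 0.5 and 0.7 the error is therefore about 0% to 5%. A lower r makes it larger, and an r above 0.7 reverses it.

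**Change from the early visit among stayers.** Replacing r by 1 gives 10^(0.4 × (0.7 − 1) × δ) = 0.97, 0.95 and 0.93. By this measure waning looks faster, not slower.

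**The case against.** The strongest reply is that the premise is not in the documents. They do not say how many subjects were vaccinated elsewhere, whether subjects knew their titers, or whether leaving was related to titer. This stands: the sizes above are conditional and the direction is open. A reader might infer that low responders left and that the plan will make durability look better than it is. The protocol reports poor neutralizing responses in transplant subjects, but nothing links titer to outside vaccination within the groups.

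Second, for a description of subjects not yet vaccinated elsewhere, the per-visit GMT is correct. The trial tests no hypothesis, and Protocol 9.4.3 calls it exploratory. This also stands, and it limits the point to interpretation; type I error and power are not involved. But the SAP does not say that this is its target, and it plans confidence intervals and joined curves that invite the wider reading.

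Third, part of this is already visible. SAP 6.1.1 gives n in every continuous summary and splits results by HIV and transplant status. Titers are listed, and so are discontinuations with reasons. That is fair, but n does not say why subjects are missing. Protocol 7.2 makes outside vaccination a reason for discontinuation only for transplant subjects.

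Fourth, one unstructured model for everyone would not fit. Weeks 3 and 7 are Group B visits only. Transplant subjects have nine post-baseline titer times over two doses, hence 9 × 10 / 2 = 45 covariance parameters for 15 people. This stands and shapes the fix.

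**Conclusion.** The point holds as a cheap improvement to a descriptive analysis. The Week 12 and Week 26 GMTs average over whoever has not been vaccinated elsewhere, and the plan has no method for the others. If leaving is related to earlier titers, these GMTs are biased for the enrolled cohort's titer without outside vaccination. Under the stated assumptions, with low responders leaving more often, the Week 26 GMT is about 8% to 18% too high. The bias is zero if leaving is unrelated to titer, and it reverses if high responders leave.

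Three stronger readings are tempting and are not supported:

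- That waning will look slower. The documents do not show who leaves, and the paired change among stayers moves the other way.
- That fold rise is affected as much as GMT. It is about 0% to 5% off for r between 0.5 and 0.7.
- That excluding titers after outside vaccination is itself an error. The exclusion is defensible, and because sampling stops, removing the rule would recover few titers. What is missing is a stated target and some use of the data collected before leaving.

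**What to change.** 1. In SAP 6.5, state whether Weeks 12 and 26 are meant to describe the enrolled cohort without outside vaccination or only subjects not yet vaccinated elsewhere.
2. Keep the observed GMT and GMFR as planned.
3. Add to SAP 6.5.1 and 6.5.2, as a supplementary analysis, a repeated-measures model on log titer using all titers before non-trial vaccination. Fit it separately for Group A (visit by arm) and for non-transplant Group B (on its own visits), with baseline log titer as a covariate and a simpler covariance as fallback. Show model-based GMT and GMFR for Weeks 12 and 26 beside the observed ones.
4. Keep the 15 transplant subjects descriptive.
5. For each visit, report the number removed because of non-trial vaccination, print n under the figures, and compare the earlier titers of leavers and stayers.

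The cost is two standard models per assay and strain and one extra table; no new data are needed. The model relies on data being missing at random given earlier titers. That cannot be verified, although a delta-shift analysis can show how far the result depends on it. Titers set to half the lower limit or twice the upper limit (SAP 6.1.3) strain the normality assumption where there are many of them.
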